7.7. Study Oversight

Safety oversight will be under the direction of Riverside's Institutional Review Board, composed of individuals with the appropriate expertise, including medical doctors, community members with a scientific background, and nurses. The IRB will conduct a comprehensive study audit and will meet at least semiannually to assess safety and efficacy data on each arm of the study. The IRB will provide its input to the study sponsor and study team.

8. Clinical Monitoring

Site monitoring is conducted to ensure that the rights and well-being of human subjects are protected, that the reported trial data are accurate, complete, and verifiable, and that the conduct of the trial is in compliance with the currently approved protocol/amendment(s), with GCP, and with applicable regulatory requirement(s). Monitoring activities include communication with the clinical investigator and study site staff; review of the study site's processes, procedures, and records; and verification of the accuracy of data submitted to the sponsor.

Clinical monitoring will be conducted by both the study sponsor and Riverside's IRB.

Riverside's IRB will conduct the following monitoring activities:

- Annual audit of data collected from the study and study files
- Annual observation of informed consent process
- Monthly review of reported adverse events and protocol deviations and performance of risk assessment to determine the need for an action plan

Stryker Spine will conduct the following monitoring activities:

- Regularly scheduled audits at critical phases of the study
- Review of complaint submissions by Stryker representatives

9. Statistical Considerations

9.1. Statistical and Analytical Plans

The general statistical plan is outlined below. A detailed statistical analysis plan (SAP) will be developed and approved by the study sponsor and study principal investigator prior to analysis.

9.2. Statistical Hypotheses

Primary Efficacy Endpoint(s):

Spinal Fusion

- Alternative Hypothesis: Implanting the Tritanium posterior lumbar cage results in satisfactory spinal fusion time in patients aged ≥ 21 years with degenerative disk disease and undergoing a spinal fusion in a one level or two contiguous levels from L2 to S1 compared to those who received PEEK implant as measured over a 6-week, 3-month, 6-month and 12month post-operative period
- Null Hypothesis: Implanting the Tritanium posterior lumbar cage does not result in an satisfactory spinal fusion time in patients aged ≥ 21 years with degenerative disk disease and undergoing a spinal fusion in a one level or two contiguous levels from L2 to S1 compared to those who received PEEK implant as measured over a 6-week, 3-month, 6-month and 12-month post-operative period

Secondary Efficacy Endpoints(s):

Questionnaires

- Alternative Hypothesis: Participants implanted with the Tritanium posterior lumbar cage
 will report higher quality of life improvement, pain improvement, and disability
 improvement scores compared to participants implanted with the PEEK AVS uniLIF Spacer
 System as measured over a 6-week, 3-month, 6-month and 12-month post-operative period
- **Null Hypothesis:** There will be no difference between the quality of life, pain, and disability scores in participants that were implanted with the Tritanium or PEEK AVS uniLIF Spacer System as measured over a 6-week, 3-month, 6-month and 12-month post-operative period

Adverse Events

- Alternative Hypothesis: There will be a difference in the number and severity of adverse
 events observed between participants who were implanted with the Tritanium posterior
 lumbar cage compared to participants who were implanted with the PEEK AVS uniLIF Spacer
 System as measured over a 6-week, 3-month, 6-month and 12-month post-operative period
- **Null Hypothesis:** There will be no difference in the number and severity of adverse events observed between participants who were implanted with the Tritanium posterior lumbar cage compared to participants who were implanted with the PEEK AVS uniLIF Spacer System as measured over a 6-week, 3-month, 6-month and 12-month post-operative period

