7.2.3. Definition of Serious Adverse Events (SAE)

An AE or suspected adverse reaction is considered "serious" if, in the view of either the investigator or sponsor, it results in any of the following outcomes: death, a life-threatening adverse event, inpatient hospitalization or prolongation of existing hospitalization, a persistent or significant incapacity or substantial disruption of the ability to conduct normal life functions, or a congenital anomaly/birth defect. Important medical events that may not result in death, be life-threatening, or require hospitalization may be considered serious when, based upon appropriate medical judgment, they may jeopardize the patient or subject and may require medical or surgical intervention to prevent one of the outcomes listed in this definition. Examples of such medical events include allergic bronchospasm requiring intensive treatment in an emergency room or at home, blood dyscrasias or convulsions that do not result in inpatient hospitalization, or the development of drug dependency or drug abuse.

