7.3. Classification of an Adverse Event

7.3.1. Severity of Event

For AEs not included in the protocol defined grading system, the following guidelines will be used to describe severity.

- **Mild** Events require minimal or no treatment and do not interfere with the participant's daily activities.
- Moderate Events result in a low level of inconvenience or concern with the therapeutic measures. Moderate events may cause some interference with functioning.
- Severe Events interrupt a participant's usual daily activity and may require systemic drug therapy or other treatment. Severe events are usually potentially life-threatening or incapacitating.

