7.5. Reporting Procedures

7.5.1. Adverse Event Reporting

Any AE that occurs during the participant's enrollment in the study will be recorded on the AE case report form. Pre-existing medical conditions or symptoms occurring prior to the initiation

of the study will not be reported as AEs, but an exacerbation of a pre-existing medical condition or symptom will be reported as an AE. Pain, neurological status, and functional impairment should be considered AEs when a participant's complaint for any of these symptoms results in an unscheduled visit and/or when a participant presents with a new or worsening symptoms as compared to a previous visit. All AEs will be followed until the event is resolved or considered to be stable.

IF an AE is ongoing when the participant completes the final visit, the AE will be followed until resolution or until 3 weeks after the final study visit has passed, whichever comes first. The study files must contain relevant source documents to confirm the occurrence of an AE and must be provided to the IRB upon request.

What Event is Reported	When is Event Reported	By Whom is Event Reported	To Whom is Event Reported
Fatal or life-threatening unexpected, suspected serious adverse reactions	Within 7 calendar days of initial receipt of information	Investigator	Local/Internal IRBStryker's Post Market Surveillance Team
		Sponsor or Designee	FDA (if IND study)
Non-fatal, non-life- threatening unexpected, suspected serious adverse reactions	Within 15 calendar days of initial receipt of information	Investigator	 Local/Internal IRBs/Institutional Officials Stryker's Post Market Surveillance Team
		Sponsor or Designee	 FDA (IND/Marketed Products) All participating investigators
Unanticipated adverse device effects	Within 10 working days of investigator first learning of effect	Investigator	Local/internal IRBsStryker's Post Market Surveillance Team
		Sponsor or Designee	FDA (if IDE study)
Unanticipated Problem that is not an SAE	Within 14 days of the investigator becoming aware of the problem	Investigator	 Local/internal IRBs/Institutional Officials Stryker's Post Market Surveillance Team
All Unanticipated Problems	Within 30 days of the IRB's receipt of the report of the UP from the investigator	IRB	• OHRP
		Investigator	• IRB

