9.3.2. Analysis of the Secondary Endpoint(s)

Improvement in SF-36, EQ-5D, ODI, and VAS scores will be compared between groups using a repeated measure ANOVA (analysis of variance).

The occurrence rate of adverse events will be assessed using a Kaplan-Meier approach and a comparison of serious adverse event rates will be made using a chi-squared analysis.

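### The adverse event hypothesis in 9.2 concerns number and severity, but no analysis in 9.3.2 uses the severity grade, and the Kaplan-Meier approach, as usually read, ignores repeat events

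*Protocol*

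**What the plan says.** Section 9.2 of the protocol gives AEs their own pair of hypotheses. The alternative is that "There will be a difference in the number and severity of adverse" events between the two devices; the null is that "There will be no difference in the number and severity of adverse events".

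Section 9.3.2 then names the analyses. For all AEs, "The occurrence rate of adverse events will be assessed using a Kaplan-Meier approach". For serious events, "a comparison of serious adverse event rates will be made using a chi-squared analysis". No other AE analysis appears in section 9.3.

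The protocol keeps severity and seriousness apart:

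- **Severity (7.3.1).** A three-step scale of mild, moderate and severe, introduced by "the following guidelines will be used to describe severity".
- **Seriousness (7.2.3).** Defined by outcome, such as death, hospitalization or incapacity: "An AE or suspected adverse reaction is considered 'serious' if, in the view of either the investigator or sponsor" one of those outcomes results.

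On data capture, 7.5.1 states: "Any AE that occurs during the participant's enrollment in the study will be recorded on the AE case report form". It also treats pain, neurological status and functional impairment as AEs when a participant "presents with a new or worsening symptoms as compared to a previous visit". Section 4.2.2 lists serious adverse events as the only AE endpoint.

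**The concern.** The hypothesis has two parts, and the named analyses do not match them.

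For severity, the only graded information is the 7.3.1 scale, and no analysis takes it as input. Seriousness is not a substitute: an event can be severe without being serious, or serious without being severe.

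For number, a Kaplan-Meier curve as usually drawn stops at each participant's first event, so one AE and six AEs count the same. The AE definition in 7.5.1 allows the same person to contribute several events over four follow-up visits. In addition, 9.3.2 says that the AE rate will be assessed, but names no test between the arms for all AEs.

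At stake is the wording of the safety conclusion. A team that follows 9.3.2 to the letter could report no difference in number and severity from analyses that never looked at grades or at repeat events.

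**Working it through.** **1. Hypothesis set against analysis**

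| Part of the 9.2 hypothesis | Data needed | Analysis named in 9.3.2 | Match |
|---|---|---|---|
| Severity | Grade from 7.3.1 | None; chi-squared uses seriousness from 7.2.3 | No |
| Number: participants with any AE | Yes/no and time of first AE | Kaplan-Meier, no between-arm test named | Partly |
| Number: AEs per participant | Count from the AE case report form | None on the usual first-event reading | No |

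The protocol gives no AE rate, effect size, significance level or power for this comparison, so there is no stated figure to reproduce. Steps 2 to 4 are illustrations only. They assume 10 per arm (5.3 gives 20 in total; equal allocation is assumed), a two-sided 0.05 level, and the log-rank test as the usual companion of Kaplan-Meier. Steps 3 and 4 use 3,000 simulated trials per scenario.

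**2. Severity: hypothetical data**

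Suppose worst grades of mild/moderate/severe are 8/2/0 in one arm and 1/3/6 in the other, and each arm has 1 SAE in 10.

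- Rank test on worst grade: p = 0.001.
- Chi-squared test on SAEs, 1/10 versus 1/10: p = 1.0.

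The named test shows nothing while the grades differ strongly.

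**3. Number: only repeat events differ**

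Both arms have the same share with any AE and the same timing of first events. Affected participants have one AE each in one arm, and on average 2 or 3 in the other.

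| Share with any AE | Log-rank, first event | Rank test on counts, 2 times | Rank test on counts, 3 times |
|---|---|---|---|
| 0.5 | 5–6% | 10% | 13% |
| 0.7 | 5–6% | 24% | 41% |
| 0.9 | 5–6% | 62% | 86% |

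The first-event test rejects at about its nominal 5%, so it carries no information on this kind of difference.

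**4. Number: the whole AE rate doubles**

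Counts are Poisson with mean m, so the share with at least one AE is 1 − exp(−m). For m = 1.5 versus 3 this is 0.78 versus 0.95; for 0.3 versus 0.6 it is 0.26 versus 0.45. The first-event analysis therefore does respond here. The last column adds a perioperative AE in half of each arm. Each cell gives approximate power for the first-event log-rank test versus the rank test on counts.

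| Mean AEs per participant | No perioperative AE | Perioperative AE in half of each arm |
|---|---|---|
| 1.5 vs 3 | 30% vs 55% | 13% vs 49% |
| 1 vs 2 | 27% vs 38% | 12% vs 32% |
| 0.5 vs 1 | 20% vs 21% | 9% vs 16% |
| 0.3 vs 0.6 | 15% vs 13% | 6% vs 9% |

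Repeat runs move these figures by about 2 percentage points. Counts gain clearly when AEs are frequent. When AEs are rare and there is no common perioperative event, the gain disappears.

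**The case against.** The strongest reply has four parts.

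**The SAP may supply the detail.** Section 9.1 calls this a general plan, with a detailed SAP to follow. Event definitions, rules for repeat events and severity tables are commonly settled there, and 9.3.2 names neither a log-rank test nor a first-event rule. This carries weight for the number part, where the first-event reading is usual but inferred. It carries less for severity: the protocol itself fixes both a hypothesis and a list of methods, and an SAP that follows 9.3.2 exactly leaves the severity part of 9.2 untested.

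**The analyses are not blind to number.** A reader might infer that they use neither number nor severity and so cannot answer the question at all. The documents do not support that. An occurrence rate is one form of AE number, and step 4 shows that a first-event test reacts when the overall rate rises.

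**AE frequency is unknown.** A reader might also infer from 7.5.1 that nearly everyone will have an early first event and the curves will converge. That is possible, but the protocol gives no rates, and the advantage of counts depends on it.

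**The consequence is limited.** This is a secondary hypothesis in a 20-participant study. The listed AE endpoint, SAEs, does have a named comparison. The halting rule in 7.6 uses graded events, and 7.7 provides for safety review by arm, so severity is not ignored in the conduct of the trial. All of this stands, and it limits the importance of the point without removing the mismatch.

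**Conclusion.** The concern holds as a mismatch between two statements in the protocol. Severity is the firm part: 9.2 puts it in the null hypothesis, 7.3.1 and 7.2.3 separate it from seriousness, and no named analysis uses the grade. This needs no assumption about rates. The number part is narrower: on the usual first-event reading, repeat AEs are ignored, and no between-arm test is named for all AEs.

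The size of the number part rests on assumed Poisson rates and 10 per arm. In the rate-doubling scenarios, the gain from analysing counts ranges from about 25 percentage points of power (55% − 30%, means 1.5 versus 3) to none (13% versus 15%, means 0.3 versus 0.6). With common perioperative events it ranges from about 36 points (49% − 13%) down to 3 (9% − 6%). Power is low under either method in most of these scenarios, so a non-significant result would say little. The gain to be had is mainly that the safety conclusion would describe what was actually analysed. It is worth correcting, but it is not critical to the trial.

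**What to change.** Choose one of the following before the data are analysed.

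1. **Extend 9.3.2 to match 9.2.** Compare AE counts per participant between arms by an exact rank or permutation test, with follow-up time reported. Compare each participant's worst grade (none, mild, moderate, severe) by an exact rank test. Keep the Kaplan-Meier curve as descriptive and state that it shows time to first AE.
2. **Narrow 9.2 to match 4.2.2 and 9.3.2.** Restate the hypothesis as occurrence of SAEs, and describe AE counts and grades without a formal test.

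Exact methods suit the sample size. For example, SAEs in 0/10 versus 4/10 give p = 0.025 by uncorrected chi-squared but p = 0.087 by Fisher's exact test.

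The cost is a few lines of wording and, under the first option, two small analyses. Section 7.5.1 already requires every AE to be recorded and 7.3.1 supplies the grade, so no new data collection is needed. The drawback of the first option is two more low-power tests of a secondary hypothesis, so their results should be read with the estimates and not by p-value alone.

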9.3. Description of Statistical Methods

9.3.1. Analysis of the Primary Efficacy Endpoint(s)

The primary endpoint analysis involves a comparison of participant fusion rates at 6-weeks, 3-months, 6-months and 12-months after surgical intervention. All participants who were enrolled will be included in this analysis. Participants will be excluded from the analysis if a CT scan and x-ray cannot be obtained at the 6-week visit.

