2.1.3. Importance of the study

2.2. Scientific Rationale

Pain originating from the spine is the second most frequent cause for visits to a physician and "ranks fifth as the reason for hospital admission" [6]. The Agency for Healthcare Research and Quality published a brief that found spinal fusion was the 6th most frequently performed surgical procedure with about 490,000 cases performed annually [Holsgrove].

It is hypothesized that the Tritanium PL Cage will result in satisfactory spinal fusion time in patients aged ≥ 21 years with degenerative disk disease and undergoing a spinal fusion in a one level or two contiguous levels from L2 to S1 compared to those who received PEEK implant as measured over a 6-week, 3-month, 6-month and 12-month post-operative period.

It is also hypothesized that participants implanted with the Tritanium PL Cage will report more improved back pain scores as measured by the Visual Analogue Scale (VAS), Oswestry Disability Index (ODI), 36-Item Short Form Survey (SF-36), Generic Health Status Survey (EQ-5D), and Press Ganey Patient Satifaction Survey.

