3.1. Primary Objective

The primary purpose of this study is to measure the efficacy of the Tritanium Posterior Lumbar Cage, by examining how robust the fusion is and how long it takes to achieve fusion of the spine. The results of this study may demonstrate that the Tritanium PL Cage is an effective option for patients that suffer from DDD.

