4.2. Study Endpoints

4.2.1. Primary Endpoint

This study's primary endpoint is time to fusion at post-operative follow-up, evaluated by radiologist interpretation of radiographic and CT imaging.

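### The primary endpoint is time to fusion, but the stated primary analysis compares fusion rates at four visits, the primary hypotheses turn on an undefined 'satisfactory' time, and missing 6-week imaging excludes randomised participants

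*Protocol*

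**What the plan says.** **Endpoint.** Protocol section 4.2.1 states that the "primary endpoint is time to fusion at post-operative follow-up, evaluated by radiologist interpretation of radiographic and CT imaging". The primary objective in section 3.1 is to be met "by examining how robust the fusion is and how long it takes to achieve fusion of the spine". The design description in section 4.1 names both the rate and the speed of fusion.

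**Hypotheses.** Section 2.2: "It is hypothesized that the Tritanium PL Cage will result in satisfactory spinal fusion time". Section 9.2 gives the alternative as "Implanting the Tritanium posterior lumbar cage results in satisfactory spinal fusion time" and the null as "Implanting the Tritanium posterior lumbar cage does not result in an satisfactory spinal fusion time", each compared with PEEK over the four visits.

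**Analysis.** Section 9.3.1: "The primary endpoint analysis involves a comparison of participant fusion rates at 6-weeks, 3-months, 6-months and 12-months after surgical intervention".

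**Population.** Section 9.3.1 continues: "All participants who were enrolled will be included in this analysis". The next sentence is: "Participants will be excluded from the analysis if a CT scan and x-ray cannot be obtained at the 6-week visit". Section 9.4.4 leaves missing radiographic data out of the primary evaluation and takes a participant without 6-week radiographic endpoints out of the study. Section 9.4.1 allows replacement of participants who discontinue by the 6-week visit without imaging. Section 5.3 sets recruitment at 20.

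**The concern.** Endpoint, hypothesis, analysis and population should describe one question. Here they do not. A SAP that follows section 4.2.1 analyses a time. A SAP that follows section 9.3.1 produces four visit-wise comparisons. Neither can use section 9.2 to say what result would support the hypothesis. In addition, membership of the primary analysis set depends on something that happens after randomisation, the 6-week imaging. Participants who miss it may differ in healing or in recovery from surgery, and their later images are left out of the primary comparison. With 20 participants, a few such losses matter.

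**Working it through.** The protocol gives no alpha, power, effect size or allocation ratio, so there is no planned figure to reproduce. The check is mainly a comparison of texts.

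**1. Endpoint against analysis.** Section 4.2.1 names one endpoint, a time. Section 9.3.1 describes rates at 6 weeks and at 3, 6 and 12 months, and names no analysis of time. Section 4.1 explains why both ideas appear but does not rank them, and section 4.2.1 names time alone.

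**2. Can the hypotheses be tested?** A testable pair needs a reference value, a margin, or a statement of no difference. 'Satisfactory' supplies none of these and is not defined elsewhere. The fusion criteria in Appendix A concern fusion status and set no time. The nulls for questionnaires and adverse events in the same section 9.2 are ordinary no-difference statements, so the primary pair is the exception.

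**3. What a missed 6-week scan costs in information** (taking fusion, once reached, as kept):
- Fused at 3 months: fusion lies between surgery and the 3-month scan. A negative 6-week scan would only have moved the lower bound to 6 weeks.
- Not fused at 3 months, fused at 6 months: fusion lies between those two scans, exactly as if the 6-week scan existed.
- Not fused at 12 months: censored at 12 months, again unchanged.

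The missed scan therefore widens the interval at most. It does not make the participant uninformative, yet the rule drops the participant.

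**4. Size from the document.** 1/20 = 5% of participants per exclusion, with up to three later scans (3, 6 and 12 months) outside the primary analysis.

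**5. Illustration only.** Assumed: 10 per arm, two-sided 0.05, and these cumulative fusion percentages at the four visits. No difference: 5/35/65/85, 10/30/60/90, 20/40/60/80. PEEK v Tritanium: 5/25/50/85 v 15/60/85/95; 5/20/45/90 v 20/60/85/90; 5/20/45/90 v 10/50/80/95. The complete-data figures come from enumerating all 1001 × 1001 pairs of arm outcomes.

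| Quantity | Three curve sets |
|---|---|
| Error, any visit p<0.05, Pearson | 8.59 / 8.38 / 11.00% |
| Error, any visit p<0.05, Fisher | 2.66 / 2.50 / 3.43% |
| Error, one exact permutation grouped log-rank | 4.18 / 4.24 / 4.54% |
| Power, exact permutation log-rank | 38.4 / 37.0 / 32.4% |
| Power, four Pearson tests at 0.05/4 = 0.0125 | 29.7 / 39.5 / 25.6% |

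With 20% of 6-week scans missing at random, power of the permutation test is:
- excluded, not replaced: 31.0 / 31.3 / 26.4%
- excluded and replaced: 38.4 / 37.0 / 32.4%, with 20/0.8 = 25 enrolled on average
- kept, with fusion assigned to the first scan that shows it: 38.0 / 36.6 / 32.3%, with 20 enrolled

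Under exclusion with replacement and no true difference, error stays at 3.9–4.5% if missingness is linked to healing alike in both arms. It reaches 6.5–7.5% if that link holds in one arm only (50% missing when unfused at 6 months, 10% otherwise).

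**The case against.** The strongest reply is that fusion is seen only at four scheduled visits. With complete scans and no loss of fusion, the four cumulative rates are the whole observable time-to-fusion distribution. Section 4.1 gives a rate comparison a stated basis, and section 9.1 calls this a general plan with a SAP to follow, so the choice of test, alpha and multiplicity control belong there. This stands as far as it goes: the absence of a named test is not a fault. It does not remove the mismatch between sections 4.2.1 and 9.3.1. It also fails once scans are missing, if leaving missing data out under section 9.4.4 means that each visit's rate is taken over those scanned at that visit.

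The all-enrolled sentence followed by an exclusion can be read as a rule with an exception. Even so, the exception is a post-randomisation exclusion.

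A reader might infer several stronger things that the text does not support:
- *Any single missed image leads to exclusion.* Section 9.3.1 names a CT scan and an x-ray together, and does not say whether lacking one is enough.
- *A late 6-week visit can get no study scan.* The bar on imaging outside a window in section 6.3.5 concerns unscheduled visits.
- *All later imaging is certainly lost.* Section 5.4.2 continues protocol follow-up procedures after withdrawal, for safety capture, and section 6.3.4 obtains CT and x-ray at early termination. What is clear is that section 9.3.1 keeps any such scans out of the primary analysis.
- *The plan inflates error or wastes power.* The illustration shows inflation with Pearson and none with Fisher. The single test is less powerful than Bonferroni–Pearson in one scenario of three. Under random missingness, power falls only without replacement.

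**Conclusion.** Three faults stand on the text, with high confidence.

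1. The primary endpoint is a time, and the stated primary analysis is of rates at four visits.
2. The primary hypotheses have no threshold, margin or direction.
3. Randomised participants without 6-week imaging are excluded from the primary analysis and removed from the study. Optional replacement restores the number but not the randomised comparison.

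The size that the document supports is 5% of the sample per exclusion. The error and power figures depend on assumed curves, alpha, allocation and missingness, and carry no part of the conclusion. These points should be settled before outcome data are seen, because a SAP faithful to sections 9.2, 9.3.1 and 9.4.4 would carry them forward.

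**What to change.** - **9.3.1:** State the primary analysis as one between-arm comparison of the time-to-fusion distribution that allows for assessment only at visits. Make visit-specific fusion proportions supportive. Leave the specific test and alpha to the SAP.
- **9.2 and 2.2:** Replace 'satisfactory' with a testable statement, such as a null of no difference between arms in the distribution of time to fusion. If another claim is meant, state its direction and margin.
- **9.3.1 and 9.4.4:** Delete the exclusion and the removal for missing 6-week imaging. Keep these participants in follow-up and analyse all randomised participants, treating a missed scan as a wider interval or as censoring at the last available scan. Use an interval-censored method unless fusion is simply assigned to the first scan that shows it. That simpler rule has a cost: in a simulation with no true difference and 30% of scans missing in one arm at the first three visits, an asymptotic log-rank test had 6.4–7.4% error, against 5.2–5.4% with complete scans. Missing 6-week scans alone caused no inflation.
- **9.4.1:** State that a replacement is additional and does not remove the original participant from the analysis.

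Cost: wording in five sections (2.2, 9.2, 9.3.1, 9.4.1, 9.4.4) and a little more analysis work, with the visit schedule unchanged. One fused/not-fused call per participant and visit must be settled before the first read, because the Appendix A list and two independent readers do not by themselves give one. Precision stays low with 20 participants, whichever analysis is chosen.
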